1.2. Background on the Study Drugs

Roluperidone is a novel cyclic amido derivative, with affinity and antagonistic activity at the 5-hydroxytryptamine-2A (5-HT_{2A}), sigma₂, α_{1A} -adrenergic, and, to a lesser extent, α_{1B} -adrenergic receptors. Its metabolite, BFB-520, has a comparable profile to roluperidone, with lower affinity for sigma₂ receptors, and lower affinity for 5-HT_{2A} receptors. Roluperidone has very low or no affinity to, or antagonistic activities on, dopaminergic, muscarinic, cholinergic, and histaminergic receptors. Hence, roluperidone mainly targets 5-HT_{2A}, sigma₂, α_{1A} - and α_{1B} -adrenergic pathways without direct blockade of dopaminergic pathways/receptors and, in particular, the D₂ dopaminergic receptor sub-type, which is the main target of most available antipsychotics to alleviate psychotic symptoms of patients afflicted by schizophrenia.

Because roluperidone lacks antagonistic activity at the D_2 receptors, it exerts its pharmacologic effect without blocking the brain's dopamine- (DA-) driven reward systems. Therefore, roluperidone does not induce secondary negative symptoms such as sedation and Parkinsonism. Unlike most antipsychotics, it does not, at therapeutic doses, increase prolactin levels or cause weight gain or akathisia.

Nevertheless, it is possible that roluperidone modulates both dopaminergic and glutamatergic pathways without blocking DA receptors, in addition to its effects on neuroplasticity and brain cholesterol metabolism (data on file). The various effects of roluperidone in the different brain areas can be explained by the complexity of the mesolimbic and mesocortical pathways and their role in schizophrenia. Moreover, the antagonist properties of roluperidone on its main targets (5-HT_{2A}, sigma₂, α_{1A} -adrenergic, and α_{1B} -adrenergic receptors) can contribute to the regulation of the imbalance between DA, glutamate, and serotonin. Indeed, these targets are involved in the modulation of the different pathways involved in positive and negative symptoms of schizophrenia.

Roluperidone is intended for the treatment of negative symptoms of schizophrenia. Roluperidone should be used as monotherapy, ie, non-adjunctively with antipsychotics. Due to a risk of QT prolongation that is known to be partly related to the CYP2D6 metabolism of metabolite BFB-520, roluperidone is only intended for patients who have at least 1 CYP2D6 allele with normal function.

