6.2. Collection of Blood

The maximum amount of blood drawn per subject in this study will not exceed 500 mL for subjects who complete the study. Repeat or unscheduled samples may be taken for safety reasons.

Table 1: Volume of Blood to be Collected from Each Subject

Type of Sample	Volume per Sample (mL)	No. of Samples per Subject	Total Volume of Blood ^a (mL)
Safety (including screening and post-treatment			
assessments)			
- Hematology	4	5	20
- Clinical chemistry ^b	8.5	5	42.5
- Genotyping	4	1	4
Pharmacokinetic samples (roluperidone / BFB-520)	2.5	70	175
Pharmacokinetic samples (olanzapine)	3	35	105
Loss by use of indwelling intravenous cannula	2	1	2
-		Total:	348.5

^a Calculated as number of samples multiplied by amount of blood per sample.

If blood samples are collected via an indwelling cannula, an appropriate amount (ie, 1 mL) of fluid slightly more than the dead space volume of the lock will be removed from the cannula and discarded before each blood sample is taken. After blood sample collection, the cannula will be flushed with 0.9% pharmaceutical grade for injection sodium chloride, or sodium heparin of 100 U/mL (where applicable) and charged with a volume equal to the dead space volume of the lock.

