6.5. Safety Evaluations

Any clinically significant abnormalities persisting at the end of the study will be followed by the investigator until resolution or until a clinically stable endpoint is reached.

The study will include the following evaluations of safety and tolerability according to the time points provided in the TIME AND EVENTS SCHEDULE.

Adverse Events

Adverse events will be reported by the subject for the duration of the study. Adverse events will be followed by the investigator as specified in Section 9.

Clinical Laboratory Tests

Blood samples for serum chemistry (collected after an overnight fast) and hematology and urine samples for urinalysis will be collected according to the TIME AND EVENTS SCHEDULE.

The investigator must review the laboratory report, document this review, and record any clinically relevant changes occurring during the study in the adverse event section of the CRF. The following tests will be performed by the designated laboratory.

• Hematology:

- hemoglobin
- hematocrit
- white blood cell (WBC) count with differential
- platelet count
- red blood cell (RBC) count

• Serum Chemistry:

- sodium
- potassium
- chloride
- magnesium
- blood urea nitrogen (BUN)
- creatinine
- glucose (fasting)
- aspartate aminotransferase (AST)
- alanine aminotransferase (ALT)
- total bilirubin
- alkaline phosphatase
- gamma-glutamyl transferase (GGT)
- creatine phosphokinase (CPK)

- lactic acid dehydrogenase (LDH)
- uric acid
- calcium
- prolactin
- phosphorous (inorganic)
- albumin
- total protein
- cholesterol (total)
- triglycerides
- high density lipoprotein (HDL)
- low density lipoprotein (LDL)

• Urinalysis

Dipstick

- specific gravity
- pH
- glucose
- protein
- blood
- ketones
- bilirubin
- Ulli uUlli
- urobilinogen
- nitrite
- leukocyte esterase

Sediment (if dipstick result is abnormal)

- RBC
- WBC
- epithelial cells
- crystals
- casts
- bacteria

If dipstick result is abnormal, the sediment will be examined microscopically.

- In women of childbearing potential, a serum pregnancy will be performed at Screening, Day -1, Day 17 and the EOS visit (refer to the TIME AND EVENTS SCHEDULE). Additional urine pregnancy tests may be conducted throughout the study, as determined by the investigator, to establish the absence of pregnancy during the study.

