1.2. STUDY MEASUREMENTS AND VISIT SCHEDULE

Phase	SCR	Admis- sion	BL		Tr	eatn	nent l	Phas	e 1						Tı	eatm	ent Pl	nase 2					EOS/ ET
Study Day	-28 to -3	-2	-1	1	2	3	4	5	6	7	8	9	10	11	12	13	14	15	16	17	18	19	31 (+2)
Informed consent	X																						
Inclusion & exclusion criteria	X		Xa																				
Demographics	X																						
Medical history/update	X		X																				
Physical examination	X		X																	X			X
Institutionalization			$\leftarrow \cdots$	• • •	• • •	• • •	• • •	• • •	• • •	• • •	• • • •	• • •	• • • •	• • • •	• • • •	• • •	• • • •	• • • •	• • • •	• • • •	\rightarrow		
Roluperidone administration				X	X	X	X	X	X	X	X	X	X	X	X	X	X	X	X	X			
Olanzapine administration											X	X	X	X	X	X	X	X	X	X			
Vital signs ^b	X		X	X	X	X	X	X	X	X	X	X	X	X	X	X	X	X	X	X	X	X	X
Weight	X		X							X										X			X
Height	X																						
Triplicate ECG ^c	X		X	X	X	X	X	X	X	X	X	X	X	X	X	X	X	X	X	X	X	X	X
CYP2D6 genotype	X ^d																						
Chemistry & hematology	X		X							X										X			X
Urinalysis ^e	X		X							X										X			X
Drug screen, alcohol test, and COVID-19	X		X																				
PK samplesf				X	X	X	X	X	X	X	X	X	X	X	X	X	X	X	X	X	X	X	
Serology	X																						
Serum pregnancy test	X		X																	X			X
FSH test	X																						
Tuberculosis test	X																						
MINI	X																						
C-SSRS	X		X	X						X	X									X			X
	X		X							X										X			X
CGI-S	X		X							X										X			X
BARS	X		X	Ì						X	X									X			X
AIMS	X		X							X	X									X			X
	X		X							X										X			X

Minerva Neurosciences, Inc.

MIN-101C18

Statistical Analysis Plan Final Version

Phase	SCR	Admis- sion	BL		Treatment Phase 1		Treatment Phase 2										EOS/ ET						
Study Day	-28 to -3	-2	-1	1	2	3	4	5	6	7	8	9	10	11	12	13	14	15	16	17	18	19	31 (+2)
Prior & Concomitant medications	X		←→							•													
Adverse events	X		←						•														

NOTE: There is no washout period between Treatment Phases.

Abbreviations: AIMS = abnormal Involuntary Movement Scale; BARS = Barnes Akathisia Rating Scale; BL = baseline; CGI-S = Clinical Global Impression – Severity C-SSRS = Columbia Suicide Severity Rating Scale; ECG = electrocardiogram; EOS = end-of-study; ET = early termination; PK = pharmacokinetics; SCR = screening; SCR = screening.

^a Verify eligibility.

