^b Vital signs include blood pressure (standing and supine), pulse, oral/tympanic temperature, and respiratory rate. During Treatment Phase 1, vital signs are assessed prior to PK sampling at pre-dose and 6 hours post-dose on Days 1-7. During Treatment Phase 2, vital signs are assessed prior to PK sampling at pre-dose and 6 hours post-dose on Days 8-17 and 24 hours after last dose of study drug is administered (eg, Days 18 and 19).

^c Three sets of triplicate ECGs (1 minute apart within 5 minutes; total of 9 ECGs are recorded at Baseline (Day -1). Other ECG assessments are recorded in triplicate prior to PK sampling. During Treatment Phase 1, ECGs are recorded at pre-dose and 6 hours post-dose on Days 1-7. During Treatment Phase 2, ECGs are recorded pre-dose and 6 hours post-dose on Days 8-17 and 24 hours and 48 hours after last dose of study drug is administered (eg, Days 18 and 19).

^d CYP2D6 genotyping to be performed.

e Urinalysis will be performed by dipstick. Urine will be sent to the laboratory for microscopic analysis only in the event that the dipstick results are abnormal.

f After vital signs and triplicate ECG. During Treatment Phase 1, PK samples for roluperidone will be obtained at time 0 (pre-dose), 1, 2, 3, 4, 5, 6, 8, 10, 12, 14, 16, 18, and 24 hours post-dose on Days 1 and 7, at 6 hours post dose on Day 2, and at pre-dose and 6 hours post-dose on Days 3-6. During Treatment Phase 2, PK samples for roluperidone and olanzapine will be obtained at 6 hours post-dose on Day 8, time 0 (pre-dose) and 6 hours post-dose on Days 9-16, and starting on Day 17 at time 0 (pre-dose), 1, 2, 3, 4, 5, 6, 8, 10, 12, 14, 16, 18, 24, 28, 32, 36, and 48 hours post-dose. If a significant prolongation in QT is observed, a PK sample should be obtained.

MIN-101C18

Statistical Analysis Plan Final Version

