3.2.4. Presentations by Time Point

Subjects are institutionalized from washout phase to Day 19 (+2 days after the last dose on Day 17). See Section 1.2 for specifics regarding when assessments are measured within a phase. The timeline of assessment measurements is repeated for each treatment phase. Assessments after screening and occurring on Day -1 after a washout period will be attributed to the following treatment phase.

Nominal Time Points as obtained from the eCRF or laboratory will be utilized for summary displays. Unscheduled visits will not be windowed and be excluded from summary tables and figures but will be listed.

If assessments are collected multiple times within a given nominal time point, the result closest to the scheduled time will be used for summary presentations. If two measurements have the same distance to the expected time, the earlier value will be used. If a scheduled assessment and an early termination assessment are collected within a given time point window, the value from the scheduled assessment will be chosen over the value from the early termination assessment.

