5.3.2. Clinical Laboratory Assessments

All laboratory parameters collected at each center's local laboratory will be standardized by converting values in original units to values in standard units and classified as normal, low, or high based on normal ranges supplied by the local laboratories and upon employing standardization.

Laboratory evaluations (including hematology, biochemistry, and urinalysis) will be listed by Treatment Phase and time point. Descriptive summaries of selected (quantitative) clinical laboratory results, and changes from Study Baseline (for Treatment Phase 1) and from Treatment Phase 2 Baseline (for Treatment Phase 2), will be presented by time point and treatment group.

The number and percentage of subjects experiencing treatment-emergent clinically significant laboratory abnormalities will be summarized by treatment group. See Table 2 for parameter specific criteria. All abnormalities that occur post-baseline, regardless of Baseline status will be included. Additionally, shifts in laboratory values with reference to the normal range from Baseline to 48 hours post-dose and from Baseline to EOS will be summarized by treatment.

Listings will be provided for subjects with any laboratory results outside the reference ranges, as well as for subjects with any potentially clinically significant (PCS) laboratory results as defined in Table 2.

Table 2. Criteria For Potentially Clinically Significant Laboratory Tests

Laboratory Parameter	SI Units	Conversion Factor ^a	Traditional Units	PCS Criteria ^b Low Values	PCS Criteria ^b High Values
Hematology	1	L		L	II.
Hemoglobin	g/L	0.1	g/dL	< 0.9 × LLN	_
Hematocrit	ratio	100	%	< 0.9 × LLN	_
White cell count	10 ⁹ /L	1	$10^3/\mu L$	≤ 2.5	≥ 15
Eosinophils absolute cell count	10 ⁹ /L	1	$10^3/\mu$ L	_	≥ 1.5
Neutrophils absolute cell count (not Black)	10 ⁹ /L	1	$10^3/\mu L$	< 1.5	> 15.0
Neutrophils absolute cell count (Black)	10 ⁹ /L	1	$10^3/\mu$ L	< 1.1	> 15.0
Lymphocyte absolute cell count	10 ⁹ /L	1	$10^3/\mu L$	< 0.75	≥ 5.0
Platelet count	10 ⁹ /L	1	$10^3/\mu L$	< 125.000	≥ 700
Chemistry	1		l .	l	I
Albumin	g/L	0.1	g/dL	< 27	
Alkaline phosphatase	U/L	1	U/L	_	≥ 2 × UNL
ALT	U/L	1	U/L	_	≥ 3 × UNL
AST	U/L	1	U/L		≥ 3 × UNL
Blood urea nitrogen	mmol/L	2.8011	mg/dL	_	> 1.3 × UNL
Calcium	mmol/L	4.008	mg/dL	< 1.97	> 2.77
Cholesterol	mmol/L	38.6698	mg/dL		> 7.75
Creatinine	μmol/L	0.0113	mg/dL	_	> 1.3 × UNL
Glucose, fasting	mmol/L	18.015	mg/dL	< 3.4	> 6.16
Potassium	mmol/L	1	mEq/L	< 3.4	> 5.3

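### SAP 5.3.2 sets the laboratory shift table at 48 hours post-dose, where no safety lab is scheduled, and names neither Day 7 nor Day 17, the only on-treatment labs

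*SAP*

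**What the plan says.** SAP 5.3.2 (Clinical Laboratory Assessments) describes the shift analysis as "shifts in laboratory values with reference to the normal range from Baseline to 48 hours post-dose and from Baseline to EOS", summarized by treatment. The proposed output is Table 14.3.5.5 in SAP section 9. Its title speaks of post-baseline shifts and names no visits.

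In SAP 1.2, the row "Chemistry & hematology" is marked at Screening, Day -1, Day 7, Day 17 and EOS/ET. The urinalysis row has the same marks, and the protocol's Time and Events Schedule agrees. Protocol 6.5 adds no other draw: chemistry "and hematology and urine samples for urinalysis will be collected according to the TIME AND EVENTS SCHEDULE". Protocol 6.2, Table 1 ("Volume of Blood to be Collected from Each Subject"), budgets five hematology and five chemistry samples.

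The schedule does contain a 48-hour time point, but for other assessments. The ECG footnote in SAP 1.2 refers to "24 hours and 48 hours after last dose of study drug is administered (eg, Days 18 and 19", and vital signs and PK samples are also marked on Day 19. SAP 3.2.4 states that "The timeline of assessment measurements is repeated for each treatment phase". It also says that summaries use nominal time points and that unscheduled visits are listed but kept out of summary tables.

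**The concern.** Safety and tolerability of the combination is the primary objective (SAP section 2), and protocol 8.5 says that laboratory data will be compared with the laboratory's normal ranges. The shift table is where the SAP tabulates that comparison. If its on-treatment target is a time at which nobody is sampled, that part of the table is empty, and what remains describes subjects who have been off both drugs for two weeks.

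The analysis is also meant to be by treatment, so it needs a visit for each treatment. Phase 1 cannot supply a 48-hour visit: olanzapine starts on Day 8 without a washout, so 48 hours after the last Phase 1 dose is Day 9, already on the combination. A programmer could not produce the table as specified and would have to pick other visits. In an open-label study that choice is better written down before the analysis.

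**Working it through.** **Lab visits against the blood budget.** The schedule rows for chemistry and hematology carry marks at Screening, Day -1, Day 7, Day 17 and EOS/ET, which is 5. Protocol Table 1 gives 5 samples of each type: 4 mL × 5 = 20 mL and 8.5 mL × 5 = 42.5 mL. With the other rows the total is 20 + 42.5 + 4 + 175 + 105 + 2 = 348.5 mL, which reproduces the stated total. A sixth safety draw would add 4 + 8.5 = 12.5 mL and give 361.0 mL. The budget therefore holds no 48-hour draw.

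**Where 48 hours post-dose falls.** Study day = dose day + 2.

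| Anchor dose | 48 hours later | Chemistry, hematology or urinalysis scheduled? |
|---|---|---|
| Day 1 (first, Phase 1) | Day 3 | No |
| Day 7 (last, Phase 1) | Day 9 | No |
| Day 8 (first, Phase 2) | Day 10 | No |
| Day 17 (last, Phase 2) | Day 19 | No |

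Intermediate doses are not useful anchors. With daily dosing, every day from Day 3 to Day 17 is 48 hours after some dose, so that reading would not pick out a visit.

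**Whether another rule fills the cell.** Unscheduled labs are excluded from summary tables (SAP 3.2.4). Early-termination labs are drawn as soon as possible (protocol 6.1.6) and belong to the EOS/ET column. The title of Table 14.3.5.5 names no time points. None of these supplies a 48-hour value.

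**What can be filled for completers.** EOS is 14 (+2) days after Day 17, so Day 31 to Day 33.

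| | As written | With Day 7 and Day 17 named |
|---|---|---|
| On-treatment lab visits with a planned shift | 0 of 2 | 2 of 2 |
| Post-baseline lab visits with a planned shift | 1 of 3 (EOS) | 3 of 3 |

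**Two related definitions.** SAP 5.3.2 measures Phase 2 laboratory changes from Treatment Phase 2 Baseline. SAP 3.2.5 spells that baseline out for ECG (pre-dose on Day 8) but not for labs. No lab is scheduled on Day 8, so the Day 7 draw is the only scheduled candidate. Separately, SAP 3.2.5 defines a treatment-emergent clinically significant laboratory abnormality by the investigator's judgement and requires that Baseline was not itself clinically significant. SAP 5.3.2 uses the same label, points to the Table 2 limits, and counts every post-baseline abnormality whatever the Baseline status. The two rules can give different counts.

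**The case against.** The strongest reply is that little is hidden. Day 7 and Day 17 results enter the by-time-point tables with changes from the phase-specific baseline, the PCS table, and Listing 16.2.8.1.5 of results outside the reference range. About 18 subjects are planned, with at least 12 completing, and that listing can be read by hand. Protocol 6.5 also requires clinically relevant laboratory changes to be recorded as adverse events, so they reach the treatment-emergent event tables by treatment group. Protocol 8.5 ties safety evaluation to the Time and Events Schedule, which suggests a slip of wording. All of this stands and limits the weight of the point. It does not make the sentence in SAP 5.3.2 workable.

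A reader might go further in three ways that the documents do not support.

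- **That on-treatment movement would show only as averages or in listings.** The by-time-point tables are indeed limited to "Descriptive summaries of selected (quantitative) clinical laboratory results", but the PCS and adverse event tables also count on-treatment abnormalities.
- **That half of the chemistry panel is uncovered, because Table 2 has limits for 12 of the 24 chemistry tests in protocol 6.5.** That count does not measure this gap. The Table 2 limits are thresholds such as three times the upper normal limit, not the normal range, so a test with a Table 2 row lacks an on-treatment normal-range shift just as one without does.
- **That prolactin is a signal bound to be missed.** Protocol 1.2 says of roluperidone: "Unlike most antipsychotics, it does not, at therapeutic doses, increase prolactin levels or cause weight gain or akathisia". The protocol's own lists of olanzapine effects (1.2 and 12.1) do not mention prolactin, and a clinically relevant rise would be reported as an adverse event.

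**Conclusion.** The shift rule is wrong as written. For completers it yields no on-treatment shift under either treatment (0 of 2 lab visits) and one shift at EOS, 14 to 16 days after the last dose. The defect lies in one planned tabulation. No data are lost, and a reader should not infer that on-treatment labs go unanalysed or that the sponsor chose to leave on-treatment shifts out. It is worth correcting because it concerns the primary objective and the correction is cheap, but it does not threaten the trial's conclusions.

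The conclusion assumes that 48 hours is counted from the first or last dose of a phase, that SAP 3.2.4 on nominal and unscheduled time points is applied as written, and that the schedule marks are read correctly. The match between five marked visits and five budgeted samples supports the last of these for blood tests. Urinalysis rests on the schedule row alone.

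The conflict between the two abnormality definitions is real but minor. Table 14.3.5.4 is titled for PCS values, and no proposed table title refers to the investigator-judged count. That list is headed as proposed, and the text of 5.3.2 does plan a treatment-emergent count, so the need is for clear labels.

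**What to change.** - **SAP 5.3.2.** Replace the 48-hour target with four shifts against the normal range: Study Baseline to Day 7 (roluperidone alone); Treatment Phase 2 Baseline to Day 17 (roluperidone + olanzapine); Study Baseline to Day 17; and Study Baseline to EOS. The second follows the convention that the section already uses for Phase 2 changes and shows movement after olanzapine is added. The third shows the cumulative picture and should be labelled so, because it carries forward any shift that arose on roluperidone alone.
- **SAP 3.2.5.** State that for laboratory tests Treatment Phase 2 Baseline is the last valid value before the first Day 8 dose, which by schedule is the Day 7 draw.
- **SAP 3.2.5 and 5.3.2 (minor).** Give separate labels to the investigator-judged treatment-emergent abnormalities and to the count of post-baseline values meeting Table 2 limits, and say which output shows each.

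The cost is SAP wording, new time points in one existing table, and one extra labelled count. No visit, sample or assessment is added. If the SAP can no longer be amended, its section 7 provides for recording the change in the clinical study report.

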3.2.5. Definitions and Terminology

Baseline Value

For quantitative safety measures, Baseline will be defined as the last valid evaluation completed before the study drug administration on Day 1. For ECG measures, including QTcF, Baseline will be defined as the mean of the triplicate set (total of 3 ECGs) performed pre-dose on Day 1 in Treatment Phase 1. This will also be referred to as Study Baseline.

A second Baseline will be used and will be referred to as the Treatment Phase 2 Baseline. For ECG, Treatment Phase 2 Baseline will be the mean of the triplicate ECGs (total of 3 ECGs) performed predose on Day 8.

Study Day

Study Day is defined relative to Day 1. Thus, the study day of an event occurring on or after Day 1 is calculated as:

Study Day = event date - date of Day 1 + 1.

The study day of an event occurring prior to Day 1 is calculated as:

Study Day = event date - date of Day 1.

Days on Study

Days on Study is calculated as Final Day on Study based on the EOS eCRF page – First Day on Study Drug + 1.

Treatment Phase Day

The study day within a treatment phase. Treatment Phase Day will be defined within each Treatment Phase 1 or 2.

Final Version

Treatment Phase Day = event date - date of Day 1 of Treatment Phase X + 1.

Study Time Point

Study Time Point is the nominal time point as recorded on the CRF.

Change from Baseline

Change from Baseline for a given endpoint is defined as the Study Time Point X value minus the Baseline Value. Change from Baseline may be study-specific (i.e., across all study phases), or Treatment Phase-specific (within any specific Treatment Phase). In the latter case, Baseline will be Treatment Phase specific.

Adverse Event

An adverse event is any untoward medical occurrence in a clinical study subject administered a medicinal (investigational or non-investigational) product. An adverse event does not necessarily have a causal relationship with the treatment. An adverse event can, therefore, be any unfavorable and unintended sign (including an abnormal finding), symptom, or disease temporally associated with the use of a medicinal (investigational or non-investigational) product, whether or not related to that medicinal (investigational or non-investigational) product.

This includes any occurrence that is new in onset or aggravated in severity or frequency from the Baseline condition, or abnormal results of diagnostic procedures, including laboratory test abnormalities.

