14.2.1.3 Clinical Global Impression- Severity Rating (CGI-S) by Treatment Phase, Safety Set

Pharmacokinetics

14.2.3.1.1	Plasma Concentrations of Roluperidone, PK Set
14.2.3.1.2	Plasma Concentrations of Roluperidone Metabolite BFB-520, PK Set
14.2.3.1.3	Plasma Concentrations of Olanzapine, PK Set
14.2.3.2.1	Plasma PK Parameters for Roluperidone, PK Set
14.2.3.2.2	Plasma PK Parameters for Roluperidone Metabolite BFB-520, PK Set
14.2.3.2.3	Plasma PK Parameters for Olanzapine, PK Set
14.2.3.2.4	Plasma PK Parameters for Roluperidone, PK Completer Set
14.2.3.2.5	Plasma PK Parameters for Roluperidone Metabolite BFB-520, PK Completer Set
14.2.3.2.6	Plasma PK Parameters for Olanzapine, PK Completer Set
Safety	
14.3.1.1	Overall Summary of Treatment-Emergent Adverse Events, Safety Set
14.3.1.2	Treatment-Emergent Adverse Events by System Organ Classification and
	Preferred Term, Safety Set
14.3.1.3	Treatment-Emergent Adverse Events by System Organ Classification, Preferred
	Term, and Maximum Severity, Safety Set
14.3.1.4	Treatment-Emergent Adverse Events by System Organ Classification, Preferred
	Term, and Maximum Relationship, Safety Set
14.3.1.5	Treatment-Emergent Adverse Events Related to Study Drug by System Organ
	Classification, Preferred Term, and Maximum Severity, Safety Set
14.3.1.6	Treatment-Emergent Serious Adverse Events by System Organ Classification and
	Preferred Term, Safety Set
14.3.1.7	Treatment-Emergent Serious Adverse Events Related to Study Drug by System
	Organ Classification, Preferred Term, and Maximum Severity, Safety Set
14.3.1.8	Treatment-Emergent Adverse Events of Special Interest by System Organ
	Classification and Preferred Term, Safety Set

Minerva Neuroscien	ces, Inc.
MIN-101C18	

Statistical Analysis Plan Final Version

14.3.1.9	Treatment-Emergent Adverse Events Leading to Discontinuation of Study Drug by
	System Organ Classification and Preferred Term, Safety Set
14.3.1.10	Treatment-Emergent Adverse Events Leading to Death by System Organ
	Classification and Preferred Term, Safety Set
14.3.5.1	Clinical Laboratory Hematology Parameters by Time Point, Safety Set
14.3.5.2	Clinical Laboratory Chemistry Parameters by Time Point, Safety Set
14.3.5.3	Clinical Laboratory Urinalysis Parameters by Time Point, Safety Set
14.3.5.4	Potentially Clinically Significant Laboratory Values Occurring Post-Baseline,
	Safety Set
14.3.5.5	Clinical Laboratory Parameter Post-Baseline Shifts, Safety Set
14.3.6.1	Vital Signs by Time Point, Safety Set

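### The SAP plans a laboratory shift to 48 hours post-dose, where no laboratory sample is scheduled; the two on-treatment draws (Day 7, Day 17) have no named shift

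*SAP*

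**What the plan says.** SAP 5.3.2 plans to summarise, by treatment, "shifts in laboratory values with reference to the normal range from Baseline to 48 hours post-dose and from Baseline to EOS". The matching output in SAP Section 9 is Table 14.3.5.5, "Clinical Laboratory Parameter Post-Baseline Shifts, Safety Set", whose title names no time points.

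The "Chemistry & hematology" row of SAP 1.2 has marks at Screening, Day -1, Day 7, Day 17 and EOS (Day 31, +2). The urinalysis row is the same, and both rows agree with the Protocol's Time and Events Schedule.

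The SAP schedule does have a 48-hour time point, but for other assessments. Its ECG footnote places ECGs at "24 hours and 48 hours after last dose of study drug is administered (eg, Days 18 and 19", and the Day 17 PK profile runs to 48 hours.

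SAP 3.2.4 uses nominal time points and adds: "Unscheduled visits will not be windowed and be excluded from summary tables and figures but will be listed".

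For changes in laboratory values, SAP 5.3.2 uses Study Baseline in Treatment Phase 1 and measures change "from Treatment Phase 2 Baseline (for Treatment Phase 2"). The rule given for that second Baseline in SAP 3.2.5 covers ECG only: "For ECG, Treatment Phase 2 Baseline will be the mean of the triplicate ECGs", taken pre-dose on Day 8.

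**The concern.** A programmer following SAP 5.3.2 literally would find no scheduled laboratory result for the 48-hour shift. The only shift left for completers is EOS, about two weeks after both drugs have stopped. The table would then show completers nothing from either treatment period.

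Safety and tolerability of co-administration is the primary objective in SAP Section 2. A table of movement against the normal range is most useful on treatment, and it should not have to be redefined at the programming stage.

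**Working it through.** **Inputs**
- Laboratory occasions: Screening, Day -1, Day 7, Day 17, EOS (SAP 1.2; Protocol Time and Events Schedule).
- Last dose of both drugs: Day 17 (SAP 1.1).
- EOS: Day 31 to Day 33, that is 14 (+2) days after the last dose (Protocol 6.1.6).
- Blood budget: Protocol 6.2, Table 1.
- Chemistry analytes: Protocol 6.5. Limits for potentially clinically significant (PCS) values: SAP 5.3.2, Table 2.

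**1. Is the five-occasion schedule right?** Protocol Table 1 budgets 5 hematology and 5 chemistry samples, which matches the five marks. Its total reproduces: 4×5 + 8.5×5 + 4×1 + 2.5×70 + 3×35 + 2×1 = 20 + 42.5 + 4 + 175 + 105 + 2 = 348.5 mL. No sixth safety draw is hidden in the budget.

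**2. Where does 48 hours fall?** Day 17 + 2 = Day 19. SAP 3.2.4 makes the same link, placing Day 19 two days after the last dose. The laboratory rows are empty on Days 18 and 19. At 48 hours the schedule holds PK, ECG and, in the Protocol, vital signs.

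**3. Could another rule supply a value?**
- An extra draw on Day 19 would be unscheduled, so SAP 3.2.4 keeps it out of the summary tables.
- The early-termination draw (Protocol 6.1.6) is taken as soon as possible, not at 48 hours, and applies only to non-completers.
- Nor is there a drug-free interval after monotherapy: "NOTE: There is no washout period between Treatment Phases". Two days after the Day 7 dose is Day 9, when olanzapine has already started.

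**4. What can be filled for completers?**

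| Shift from Baseline to | Named in SAP 5.3.2 | Scheduled sample |
|---|---|---|
| Day 7 (roluperidone alone) | No | Yes |
| Day 17 (roluperidone + olanzapine) | No | Yes |
| 48 hours post-dose (Day 19) | Yes | No |
| EOS (Day 31–33) | Yes | Yes |

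Of the 2 named shifts, 1 can be filled. Of the 2 on-treatment draws, 0 have a named shift. The EOS lag is 31 − 17 = 14 days to 33 − 17 = 16 days.

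**5. Which analytes depend on this table?** Protocol 6.5 lists 24 serum chemistry analytes and SAP Table 2 gives PCS limits for 12 of them. The other 24 − 12 = 12 are chloride, magnesium, GGT, CPK, LDH, uric acid, prolactin, phosphorus, total protein, triglycerides, HDL and LDL. Prolactin is a property on which Protocol 1.2 contrasts roluperidone with most antipsychotics, and low magnesium is an exclusion criterion (Protocol 4.3, criterion 24).

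**6. After the correction.** Shifts to Day 7, Day 17 and EOS all rest on scheduled samples: 3 of 3.

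**The case against.** The strongest reply is that this is one stray time label in a supplementary, descriptive table. Protocol 8.5 asks only that laboratory data be compared with normal ranges and that PCS frequencies be tabulated; it does not ask for a shift table. Day 7 and Day 17 are covered by Tables 14.3.5.1 to 14.3.5.3 (values and changes by time point), by the PCS table 14.3.5.4, where several criteria are multiples of a reference limit, and by the out-of-range listing 16.2.8.1.5. With about 18 subjects, individual movements can be read from listings. There is one on-treatment draw per phase, so little room exists for a selective choice, and SAP Section 7 requires deviations to be documented in the clinical study report.

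Most of this stands, and it keeps the point minor. It does not make the 48-hour shift computable. The PCS table also leaves out half the chemistry analytes. SAP 3.2.5 defines an investigator-judged abnormality that could include them, but that records clinical judgement, not movement across a reference limit. The general title of Table 14.3.5.5 would allow Day 7 and Day 17 to be added, but the text does not specify them.

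Four stronger readings are tempting, and the documents do not support them:
- **A reader might infer that the on-treatment laboratory data go unreported.** The tables and listings above show otherwise.
- **A reader might infer that the Baseline of the shift is undefined.** SAP 3.2.5 defines Baseline for quantitative safety measures as the last valid evaluation before dosing on Day 1, and 5.3.2 names the Phase 2 Baseline when it means that one.
- **A reader might multiply the mismatch by counting 48 hours from other doses.** The documents attach 48 hours to the last dose. For the same reason, the label cannot be rescued by counting from the Day 5 or Day 15 dose, although Day 7 and Day 17 follow those by two days.
- **A reader might infer that laboratory findings up to EOS are all assigned to the combination.** The rule assigning events to the most recent treatment (SAP 3.2.5) is written for adverse events only.

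**Conclusion.** The SAP is wrong as written on this point, and the error is minor. It specifies a laboratory shift that the sampling schedule cannot supply. For completers, 1 of the 2 named shifts can be filled, at 14 to 16 days after the last dose, and 0 of the 2 on-treatment draws has a named shift. The practical loss is confined to on-treatment movement against the normal range in a summary table, and it matters most for the 12 of 24 chemistry analytes with no PCS limit.

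A smaller related gap is that the SAP uses a Treatment Phase 2 Baseline for laboratory changes without saying which draw it is. Day 7 is the last scheduled draw before olanzapine starts on Day 8 and so the natural choice, but it is not written down.

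The conclusion assumes that 48 hours means the time after the last dose, as elsewhere in the documents, and that no laboratory draw is taken outside the published schedule.

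**What to change.** In SAP 5.3.2 and the shell of Table 14.3.5.5:
- Replace the 48-hour shift with Study Baseline to Day 7 (roluperidone alone) and Study Baseline to Day 17 (roluperidone plus olanzapine).
- Keep the EOS shift and label it as follow-up.

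In SAP 3.2.5, state that the Treatment Phase 2 Baseline for laboratory tests is the Day 7 draw.

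The cost is SAP wording and minor table-shell work, with no protocol amendment, visit or sample. One limitation should be footnoted: the Day 17 shift from Study Baseline reflects both drugs together, not olanzapine alone. If the SAP can no longer be revised, the replacement should be documented in the clinical study report under SAP Section 7.

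Adding a Day 19 draw is the weaker option. It needs a protocol amendment and 4 + 8.5 = 12.5 mL more blood (348.5 to 361.0 mL, within the 500 mL limit), and it would still give no shift for roluperidone alone.
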